Participants and Criteria: Patients will be identified from the Mayo Clinic Rochester, MN Pulmonary Division. Patients who either are referred to enroll in pulmonary rehabilitation at Mayo Clinic in Rochester or who are referred for nursing education regarding pulmonary rehabilitation enrollment will be approached. **Recruitment:** A study referral reminder will be incorporated into the pulmonary rehabilitation referral and pulmonary rehabilitation nursing education referrals. **Inclusion/Exclusion criteria:** Eligible patients will be aged 18 years or older, referred for pulmonary rehabilitation, and consenting to research. **Retention strategy:** Patients will be given remuneration for completing the 3 to 6 month follow-up appointment. **Methods:** This is a single-center, prospective trial examining the effects of pulmonary rehabilitation on frailty and frailty characteristics and associations between patient characteristics and improvement in frailty characteristics. Patient will be approached for recruitment in a private setting regarding willingness to participate in the study by the principal investigator or other authorized study personnel and consented with IRB-approved consent procedure and written consent form. Patients will receive a full explanation of all procedures, risks, benefits, and alternatives and all questions will be answered. Once consented patient will undergo physiologic testing and complete questionnaires. Activity monitors will be sent with patients (including a return addressed envelope with postage) to assess one week of measured activity. At three to six months physiologic testing and activity monitor recordings will be repeated. Patients will also be asked to specify the number of completed pulmonary rehabilitation sessions. **Data: Medical Record Abstraction** Patient demographics, pulmonary diagnoses, weight, height, and pulmonary function tests will be recorded. **Physiologic Measurements and Testing: Grip strength** will be measured using a Jamar Digital Hand Held Dynamometer. Three serial measurements will be taken (using the dominant hand), averaged, and adjusted by gender and BMI using normative table. **Gait Speed** will be measured using a wireless infrared timing system. Self-selected walking speed over a distance of 15 feet will be averaged over 3 trials and then adjusted for gender and height. **Dual Energy X-ray Absorptiometry (DEXA) scan** will determine body composition (body mass, fat mass and fat-free mass) at baseline and at 3-6 months following initiation of pulmonary rehabilitation. **State-of-the-art activity monitors (Sensewear Armband, Body media, Pittsburgh,PA)** will quantify kcals burned, active and sleep time, as well as quality of sleep (baseline and 3 to 6 months following initiation of pulmonary rehabilitation).

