
Questionnaires

Name of questionnaire	abbrev	Purpose of questionnaire	N of items	Cronbach's alpha
Mischel Uncertainty in Illness Scale	MUIS	Uncertainty in illness measure	33	0.65-0.90
Positive Affect Negative Affect Schedule	PANAS	Positive and negative affect	20	0.84-0.90
Chronic Respiratory Questionnaire	CRQ	Disease-specific quality of life measure in lung disease	20	0.84
Short form Health Survey-26	SF-36	Exhaustion question only	1	0.82-0.95

Sample size A convenience sample of consecutive prospective consenting patients will be enrolled. This is a pilot study and therefore sample size calculations are not required. However, in order to inform our enrollment we have made the following calculations: **Change in grip strength.** A sample size of 40 per sample will have 80% power to detect a difference in means of 20%, assuming a baseline mean of 28 in women and a standard deviation of 6.3 (as reported for females age range 50-59), using a paired t-test with a 0.05 two-sided significance level.(17) However, given an estimated prevalence of frailty of 17% we would like to recruit at least 100 patients to further study frailty in a larger sample. Based on annual pulmonary rehabilitation participants at Mayo Clinic in Rochester (~150 patients), annual referrals for nursing pulmonary education (~250-300 patients), and a recruitment rate of 80% for similar studies, we feel this is realistic.

Quality Assurance / Quality Controls:

Data abstraction Spreadsheet will be standardized (for definitions and protocol) and audited by PI weekly to ensure selection criteria and protocol compliance and monthly for completion and accuracy.

Personnel training All personnel will be trained to perform the hand grip and gait speed assessments.

Analysis plan:

Patient demographic characteristics will be summarized by mean, median and standard deviation and range (continuous variables) and counts and percents (categorical variables). A two-tailed p < 0.05 will be considered statistically significant. Frail performance will be defined as a performance of <20% predicted on physiologic tests. Pre- and post- intervention

tests will be compared using Wilcoxon Signed Rank or paired t-test as appropriate. Subgroup analysis will be performed for frail patients and those completing > 6 and > 12 pulmonary rehabilitation sessions.

Budget

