Primary expenses of this project include personnel time, statistical support, and participant remuneration. [name] lab will provide use of the activity monitors. [name] has necessary equipment for gait speed and grip strength determinations. Funding is provided by the Nelson Benefactor Career Development Award.

Timeline: The proposed study enrollment will be completed in the 9 months with most follow-up assessments completed in the one-year time frame.

Protection of human subjects:

Recruitment Procedures will be approved by the Mayo Institutional Review Board.

Data and materials A potential risk is loss of confidentiality. Data will be transferred into a password-protected database in a password-protected computer. Questionnaires will be coded without identifying features and will be stored in a locked cabinet. All data will be reported in composite form.

Physiologic Testing Another potential risk is discomfort, desaturation, or tachycardia during physiologic testing. Subjects will be monitored for adverse symptoms. Supplemental oxygen at the patient's usual settings will be allowed during testing. Clinical emergency response teams provide emergency medical coverage for the CRU and clinical area of Gonda 18. We estimate the risk to patient to be equivalent to daily activities.

Potential benefits Potential benefits of this study include improved knowledge of the benefits of pulmonary rehabilitation and knowledge of frailty performance characteristics.

Inclusion of women, minorities and children: Children will not be represented as frailty risks and pulmonary rehabilitation interventions differ. Our study will include women and minorities. No vulnerable group will be specifically targeted. We expect the minority population to mirror census data. Due to the demographics of the Southeast Minnesota area our targets are 2% black, 2% Asian, 4.5% Hispanic and 4.5% 'other' for an ideal target of 13% minority participation. Of course, health disparities occur in minority use of healthcare services so discrepancies may occur. In order to ensure that women and minorities will be appropriately represented and that the study population will be representative of all eligible patients, the PI will ensure that patients being considered meet criteria and no additional exclusions are applied.

Resources, environment, and personnel

Office space

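### The stated 80% power for a 20% change in grip strength with 40 pairs does not follow from the plan's own inputs; a paired t-test on those inputs gives at least 97%

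*Combined protocol and SAP*

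**What the plan says.** The Sample size paragraph notes that a pilot does not require a sample size calculation, but offers one anyway: "in order to inform our enrollment we have made the following calculations". The calculation concerns grip strength, and its claim reads: "A sample size of 40 per sample will have 80% power to detect a difference in means of 20" percent. The planning values behind that claim are given as follows: "assuming a baseline mean of 28 in women and a standard deviation of 6.3 (as reported for females age range 50-59"). The method is named at the end of the same sentence: "using a paired t-test with a 0.05 two-sided significance level".

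The next sentence sets the recruitment aim on a different ground, an estimated 17% prevalence of frailty: "we would like to recruit at least 100 patients to further study frailty in a larger sample".

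The Analysis plan is also paired: pre and post "tests will be compared using Wilcoxon Signed Rank or paired t-test as appropriate". The document gives no SD of the pre-to-post change, no pre/post correlation and no allowance for missing follow-up in the calculation.

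**The concern.** A shift of 5.6 against an SD of 6.3 is a large standardised effect, and 40 pairs is far more than a paired test needs to detect it with 80% power. The stated power therefore looks too low for the stated effect, or the effect too large for the stated power.

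This is the only detectable effect in the document, and change in grip strength is an Aim 1 outcome. The central hypothesis is that current rehabilitation does not address frailty characteristics optimally, so a finding of no change may be read as support for it. To judge such a result, a reader needs to know how small a change the study could have detected. The sentence suggests that 40 pairs can only just detect 20%; on the plan's own inputs they detect considerably less.

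**Working it through.** **Inputs, all from the Sample size paragraph.** 40 pairs; baseline mean 28; SD 6.3; difference 20%; paired t-test; two-sided 0.05; stated power 80%. The pre/post correlation r is not given, so I treat it as an assumption and vary it.

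**Formulas.** Difference δ = 0.20 × 28 = 5.6. Exact power comes from the noncentral t distribution with n − 1 = 39 degrees of freedom and noncentrality (δ / SD of change) × √n. If 6.3 is the between-person SD and is the same at both visits, SD of change = 6.3 × √(2(1 − r)).

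**Attempt to reproduce 80%.**

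| Reading of 6.3 | SD of change | Power, 40 pairs | Pairs for 80% |
|---|---|---|---|
| Between-person, r = 0 | 8.91 | 97.2% | 22 |
| Between-person, r = 0.25 | 7.72 | 99.4% | 17 |
| Between-person, r = 0.5 | 6.30 | 99.98% | 12 |
| SD of the paired differences | 6.30 | 99.98% | 12 |

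The last two rows coincide because √(2 × 0.5) = 1. Power rises further for r above 0.5. The stated 80% is not reproduced.

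**What 80% would require.** With 40 pairs, 80% power corresponds to δ / SD of change = 0.4543. So SD of change = 5.6 / 0.4543 = 12.33, and r = 1 − 12.33² / (2 × 6.3²) = −0.91. That would mean that the strongest patients at baseline tend to be the weakest at follow-up, which is not credible for repeated grip measurements.

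**Other readings.**
- Wilcoxon signed rank test, also allowed by the Analysis plan: 96.4% at r = 0 (4,000 simulated normal samples of 40 pairs).
- Larger SD at follow-up, 1.2 × 6.3 = 7.56, with r = 0: SD of change √(6.3² + 7.56²) = 9.84, power 93.9%.
- Unpaired t-test, 40 per group: 97.5%.
- Unpaired t-test, 20 + 20: 78.2% (80.3% by normal approximation). Close, but it contradicts both the paired test and 40 per sample.
- Paired t-test, 10% change (2.8), SD of change 6.3: 78.3% (normal approximation: 39.7 pairs for 80%). Close, but it contradicts the stated 20%.

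The two near matches imply different slips: one a wrong test and n, the other a detectable change stated at twice its size. The text does not decide between them.

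**Change detectable with 80% power, as a percentage of 28** (100 × d × SD of change / 28, where d is the standardised difference giving 80% power).

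| Complete pairs | d | SD of change 6.3 (r = 0.5) | r = 0 | r = 0.9 |
|---|---|---|---|---|
| 40 | 0.454 | 10.2% | 14.5% | 4.6% |
| 60 | 0.368 | 8.3% | 11.7% | 3.7% |
| 80 | 0.317 | 7.1% | 10.1% | 3.2% |
| 100 | 0.283 | 6.4% | 9.0% | 2.8% |

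For 40 pairs, r = 0.25 gives 12.5% and r = 0.8 gives 6.5%.

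**The case against.** The best defence is that nothing depends on the figure. The study is a pilot, the plan disclaims the need for a calculation, and the number 40 is at once replaced by a target of at least 100 justified by frailty prevalence. Feasibility is argued separately, from referral volume and recruitment rate. No enrolment number, endpoint or test changes when the sentence is corrected. All of this stands and limits the weight of the point. It does not make the sentence right, since the plan offers it expressly to inform enrolment.

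A second objection is that the 97% floor requires equal SDs at the two visits. That is so. It is the natural reading because the plan gives one SD, and an SD 20% larger at follow-up still leaves 93.9% at zero correlation.

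A third is that saying power is understated assumes the 20% is correct. If a 10% change was meant, 80% is about right and the error lies in the effect. This is fair: power is understated only if the 20% is taken at face value. Under either paired reading, 40 pairs are enough for a 20% change, so the error does not leave the study too small for it.

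**Conclusion.** The concern holds. On the plan's stated effect, SD, test and level, 40 pairs give between 97.2% power (correlation 0) and 99.98% (SD of change 6.3), and more for correlations above 0.5, against the stated 80%. This rests on reading the 20% as a share of the baseline mean, on 6.3 being either the SD of change or a between-person SD common to both visits, and on a non-negative correlation. No reading consistent with the text comes near 80%.

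What cannot be settled from the document is which of power, number of pairs and detectable change was misstated. The practical effect is on interpretation, not on study size: the plan's only statement of detectable change is unreliable, while the recruitment target stands on other grounds.

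**What to change.** State the assumed SD of the pre-to-post change, label it as an assumption, and rewrite the sentence so that power, number of pairs and detectable change agree. If the sponsor keeps 40 pairs and 80% power, one possible wording is:

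*With 40 complete pairs, a paired t-test (two-sided 0.05) has 80% power to detect a mean change of about 10% of baseline if the SD of the paired differences is 6.3 (about 14.5% to 4.6% for pre/post correlations of 0 to 0.9 if 6.3 is the between-person SD).*

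If the sponsor instead meant another effect, n or test, it should correct that figure and show the calculation.

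If a figure is added for the recruitment target, tie it to the number of complete pairs expected, using the last table above. Not all 100 recruits can be assumed to give a pair; the Timeline section plans "with most follow-up assessments completed in the one-year time frame".

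Add one line saying that the inputs are unadjusted values for women aged 50-59. The study enrols all adults, and its grip measure is processed differently: "Three serial measurements will be taken (using the dominant hand), averaged, and adjusted by gender and BMI using normative table".

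The cost is a change of wording and figures in one paragraph. The enrolment target, the tests and the procedures stay as they are.

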Frailty is defined as a decreased resistance to disability and illness. It is common (as high as 17% in advance lung disease) and associated with important patient outcomes of mortality, hospitalization, and need for nursing home.(1, 2) Frailty consists of a constellation of three or more of the following characteristics: wasting, exhaustion, decreased physical activity, slowness, and weakness.(3) Patient’s with one or more characteristics are considered “pre-frail” and those with three or more are considered “frail.” Wasting is defined as unexplained weight loss or decrease in lean body mass. It is typically measured by body composition. Exhaustion is typically measured by self-report via questionnaire. Physical activity can be self-reported through questionnaires or, more accurately, directly measured by physical activity monitors. Slowness is typically measured by gait speed (the time it takes an individual to walk 15 feet). Finally, weakness can be measured by respiratory muscle function or hand grip strength. Measures are typically adjusted for sex and height or weight and compared to expected normative values.

Little is known about frailty in patients with chronic lung disease. Emerging evidence suggests that frailty is important for both mortality and disease-specific outcomes in lung disease patients. Evidence demonstrates the above-referenced frailty characteristics are common in chronic obstructive pulmonary disease (COPD). For example, patients with COPD have been noted in separate studies to have wasting(8, 9), fatigue(10), lower physical activity(11), slower gait speed(12), or decreased strength (13). In addition, wasting has been associated with COPD mortality, and increased fatigue has been associated with increased COPD hospitalizations.(8, 10). These studies suggest the possible importance of the frailty phenotype in COPD. In addition, a mixed measure of frailty with functional and sensory deficits that found the mixed measure is associated with increased shortness of breath, health care utilization and disabilities in COPD.(15) A similar constellation of deficits was associated with an increased mortality at 12 years in patients with COPD.(16) Finally, this candidate has demonstrated that frailty is associated with increased mortality and hospitalization in COPD. (see

“Does pulmonary rehabilitation improve frailty in chronic lung disease?”

Principal Investigator (Last, First Middle): [name]

Updated: 6/23/2015

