preliminary data) Less is known about other chronic lung diseases and frailty. However, this candidate demonstrated that low muscle index (wasting) pretransplant is associated with worse survival and increased primary graft dysfunction following lung transplantation. (see preliminary data) Lung transplant candidates are typically a mixed representation of several chronic lung diseases, therefore, suggesting importance of frailty beyond COPD.

In the above mentioned preliminary data, research participants underwent pulmonary rehabilitation. Despite this frailty and frailty characteristics persisted. This suggests that pulmonary rehabilitation alone may be *insufficient* to address frailty in its current form. Prior studies have attempted to identify patient factors that lead to success in pulmonary rehabilitation. (14) It is unknown if such factors will be important to successful improvement in frailty characteristics.

Proposed methodology

We propose a single-center, prospective cohort study with **Aim 1**: measurements of frailty characteristics pre- and post-pulmonary rehabilitation referral and **Aim 2**: measurements of baseline affect, uncertainty, and demographics to examine associations between patient characteristics and improvements in frailty characteristics.

Outcomes

Aim 1: Outcomes will include median change in grip strength, gait speed, physical activity, and body composition and comparison of pre and post self-reported exhaustion. In addition, prevalence of frailty and pre-frailty will be compared pre and post pulmonary rehabilitation. **Aim 2**: Associations of positive or negative affect, baseline measure of uncertainty, and demographic factors and median or percent change in frailty characteristics.

Summary of background and significance:

Frailty is common in advanced lung disease and is associated with decreased time to hospitalization, increased length of hospital stay, and increased mortality. In addition, in lung transplant patients frailty is associated with increased primary graft dysfunction and mortality. There is a knowledge gap regarding effective interventions to treat frailty and frailty characteristics. Pulmonary rehabilitation is widely available and utilized in patients with moderate to severe lung disease. Whether pulmonary rehabilitation improves frailty is unknown.

Alignment with career goals:

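### The only frailty cutpoint for a single test, under 20% of predicted, is a grip below 5.6 on the one norm printed (3.56 SD below its mean); read as written, it would mark few patients as weak unless the cohort is very weak

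*Combined protocol and SAP*

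**What the plan says.** The Analysis plan section sets one numerical rule for a single test: "Frail performance will be defined as a performance of <20% predicted on physiologic tests". No other section gives a numerical cutpoint for grip, gait speed, activity, exhaustion or wasting. Elsewhere there is only the count rule. Background and significance says: "Frailty consists of a constellation of three or more of the following characteristics", and calls a patient with at least one characteristic pre-frail.

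Three parts of the plan depend on who is classed as frail:

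- Outcomes, Aim 1: "prevalence of frailty and pre-frailty will be compared pre and post pulmonary rehabilitation".
- Analysis plan: "Subgroup analysis will be performed for frail patients".
- Sample size: "given an estimated prevalence of frailty of 17% we would like to recruit at least 100 patients".

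The only normative mean and SD printed are in Sample size: "assuming a baseline mean of 28 in women and a standard deviation of 6.3", for women aged 50-59. Units are not stated. Under Specific Aim #1, grip is to be scored against a table by gender and BMI, which is not reproduced. Gait speed is to be adjusted for gender and height, with no norm given. The same heading for physiologic measurements also covers DEXA and activity monitoring.

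**The concern.** A threshold of 20% of predicted is a very different rule from the 20th percentile of a norm, or from a shortfall of more than 20% against predicted. The plan writes the first. Either of the others would give a usable item, and nothing in the documents says that one of them is meant.

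If an analyst codes the sentence as it stands, the weakness item may be almost empty. A patient who is clearly weak against the norm would not count as weak, and one fewer item would be available to reach the three needed for frailty. At stake are the frailty prevalence before and after rehabilitation and the frail subgroup, in a study that set its recruitment target with 17% frailty in mind. If an analyst instead guesses the intended meaning, the cutpoint would be chosen at analysis, possibly after the data have been seen.

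**Working it through.** The plan gives no expected number of patients below the cutpoint, so there is no stated figure to reproduce. I apply the rule to the printed norm and then to assumed weaker cohorts, using a normal model throughout.

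**Inputs from the documents:** mean 28 and SD 6.3 (Sample size); 20% (Analysis plan). **Assumed:** patient means and SDs, because none are given.

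**1. The cutpoint on the printed norm**

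- Literal: 0.20 × 28 = 5.6; z = (5.6 − 28)/6.3 = −3.556; share below = 0.019%.
- 20th percentile: 28 − 0.8416 × 6.3 = 22.7; share below = 20%.
- Below 80% of predicted: 0.80 × 28 = 22.4; z = (22.4 − 28)/6.3 = −0.889; share below = 18.7%.

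The 5.6 here happens to equal the difference used in the power statement ("80% power to detect a difference in means of 20" percent), because both are 20% of 28. The two uses are unrelated.

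**2. Weaker cohorts, SD kept at 6.3**

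- Mean 1 SD lower, 28 − 6.3 = 21.7: z = (5.6 − 21.7)/6.3 = −2.556; 0.53% weak.
- Mean 2 SD lower, 28 − 12.6 = 15.4: z = (5.6 − 15.4)/6.3 = −1.556; 5.99% weak.
- Mean needed for 20% to score weak: 5.6 + 0.8416 × 6.3 = 10.9, and 10.9/28 = 39% of the norm.

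**3. Direction of the effect on the item count**

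Since 5.6 < 22.4 < 22.7, anyone weak under the literal rule is also weak under both other readings. The literal rule can therefore remove a weakness item but never add one. The frail count can only fall or stay the same.

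**4. Change in the weakness item after a 20% gain in mean grip (SD fixed at 6.3)**

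| Cohort mean before → after | Literal rule, % weak | Fall per 100 | 20th percentile, % weak | Fall per 100 |
|---|---|---|---|---|
| 21.7 → 26.04 | 0.53 → 0.06 | 0.5 | 56.3 → 29.8 | 26.5 |
| 15.4 → 18.48 | 5.99 → 2.05 | 3.9 | 87.7 → 74.8 | 12.8 |
| 12.0 → 14.4 | 15.5 → 8.1 | 7.4 | 95.5 → 90.6 | 4.9 |
| 10.9 → 13.08 | 20.0 → 11.7 | 8.3 | 96.9 → 93.7 | 3.3 |

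Falls are computed before rounding. In the first two cohorts the literal item registers fewer changes. In the last two the order reverses. If instead every patient's grip rises by 20%, the SD also rises, to 1.2 × 6.3 = 7.56. The first row then becomes 0.53% to 0.34% against 56.3% to 32.9%.

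**5. Do the two workable readings agree?**

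They are equal when 0.8416 × CV = 0.20, that is, CV = 23.8%. The printed norm has CV 6.3/28 = 22.5%, so they nearly coincide there. Nothing shows that they do for gait speed or for other strata.

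**The case against.** The strongest reply is that nobody would apply the rule literally. The plan compares patients with normative values, expects 17% frailty and plans a frail subgroup, so a team with those expectations would notice a cutpoint that catches almost no one. The likely meanings also nearly agree for the printed grip norm. This makes a drafting slip plausible, but it does not settle which threshold applies, and the two candidates separate wherever the norm's CV is not close to 24%. The sentence still has to be replaced.

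The second reply is reach. The norm is one stratum, while all adults aged 18 or older are eligible, and everything beyond the reference women rests on assumed means and SDs. No gait norm is given, so any effect on the slowness item is inference. Exhaustion and wasting may lie outside the rule. All of this stands, and it limits the size of the claim. That the plan says "This is a pilot study and therefore sample size calculations are not required" does not answer the point, because frailty status is still a planned outcome.

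A reader might infer that the literal rule makes the pre/post frailty comparison generally less sensitive to gains in grip. The documents do not support that. The calculation concerns the weakness item, not the three-of-five composite, and even for the item the order reverses at cohort means of about 11 to 12. Such cohorts would be extreme, but no patient grip data are given to exclude them.

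**Conclusion.** The cutpoint is wrong as written and should be fixed. On the one printed norm it is 5.6, 3.56 SD below the mean, and 0.019% of reference women fall below it, against about 19% to 20% under either workable reading. That arithmetic is certain given the printed figures and a normal model. For patients, the share scored weak is 0.5% or 6.0% in assumed cohorts averaging 1 or 2 SD lower, and a mean near 39% of the norm would be needed to reach 20%.

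The direction is also firm: applied literally, the rule can only lower or leave unchanged frailty prevalence and the size of the frail subgroup. By how much cannot be derived from the documents. A reader might conclude that the frail subgroup would be empty or that 17% could not be reached. That does not follow, since frailty can be met through other items. Nor is the direction fixed for pre-frailty if the categories are exclusive, because a patient who loses an item can move from frail to pre-frail.

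The continuous pre/post comparisons of grip, gait speed, activity and body composition do not use the cutpoint and are unaffected.

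**What to change.** Before analysis, replace the sentence with the threshold actually intended. If it is a percentile, for example: *Frail performance is a value below the 20th percentile of the normative values (sex- and BMI-specific for grip strength, sex- and height-specific for gait speed), with the same cutpoints at baseline and follow-up.* If a shortfall of more than 20% is meant, write *below 80% of predicted* instead, again with the same cutpoints at both visits. The choice must be stated, because the readings need not agree outside the printed stratum.

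Also list the tests the rule covers, saying whether DEXA and activity measures are among them, and give the threshold for each frailty item it does not cover.

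The cost is one sentence and a short list. Grip and gait speed are recorded as continuous values, so nothing new has to be collected and patients can be scored under whichever threshold is stated.

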Does Pulmonary Rehabilitation
Improve Frailty in Chronic Lung
Disease?

NCT02512874

June 23, 2015

Introduction and Specific Aims

Frailty is defined as a decreased resistance to disability and illness. The prevalence of frailty is reported to be around 14% in elderly community populations and 17% in advanced heart and lung disease patients.(1, 2) Frailty consists of a constellation of three or more of the following characteristics: wasting, exhaustion, decreased physical activity, slowness, and weakness.(3) Patient’s with one or more characteristics are considered “pre-frail” and those with three or more are considered “frail.” Frail and pre-frail states are associated with mortality, increased falls, nursing home placements, and hospitalizations in the geriatric general population.(3-6) Frailty is also an important predictor of disease-specific outcomes in those with certain co-morbid conditions such as heart failure and osteoporosis.(3, 4, 7)

Little is known about frailty in patients with chronic lung disease. Emerging evidence by the candidate and others suggests that frailty is important for both mortality and disease-specific outcomes in lung disease patients. Preliminary evidence demonstrates the above-referenced frailty characteristics are common in chronic obstructive pulmonary disease (COPD).(8-13). In addition, this candidate has demonstrated that frailty is associated with increased mortality and hospitalization in COPD. (see preliminary data) Less is known about other chronic lung diseases and frailty. However, this candidate demonstrated that low muscle index (wasting) pretransplant is associated with worse survival and increased primary graft dysfunction following lung transplantation. (see preliminary data)

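### The frail-subgroup pre/post comparison retests the measures that define frailty, so regression to the mean biases it toward improvement; the size depends on retest correlation, which the documents do not give

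*Combined protocol and SAP*

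**What the plan says.** - Combined protocol and SAP, Analysis plan: pre- and post-intervention "tests will be compared using Wilcoxon Signed Rank or paired t-test as appropriate", with significance at a two-tailed 0.05. The section ends with "Subgroup analysis will be performed for frail patients and those completing > 6 and > 12 pulmonary rehabilitation sessions". It does not name the test used in the subgroup or say at which visit frailty is classified.
- Introduction and Specific Aims (repeated in Background and significance): frailty is a "constellation of three or more of the following characteristics: wasting, exhaustion, decreased physical activity, slowness, and weakness".
- Outcomes, Aim 1: "Outcomes will include median change in grip strength, gait speed, physical activity, and body composition", together with pre and post self-reported exhaustion. These are the five characteristics that define frailty. The same section adds that "prevalence of frailty and pre-frailty will be compared pre and post pulmonary rehabilitation".
- Analysis plan: "Frail performance will be defined as a performance of <20% predicted on physiologic tests". The text does not link this to the three-of-five count.
- Sample size: "given an estimated prevalence of frailty of 17% we would like to recruit at least 100 patients". The grip calculation is made "assuming a baseline mean of 28 in women and a standard deviation of 6.3", seeking a 20% difference.
- Proposed methodology and Specific Aim #1 (Methods): a single cohort, one baseline assessment and one repeat at three to six months. Grip and gait are each averaged over three trials at a visit.

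**The concern.** A patient enters the frail group partly because some measures happened to be low on the day. At the next visit the chance part is redrawn, so the group's average rises even if nobody has changed. A paired test compares that average with zero and counts the drift as improvement. A comparator would show the same drift and a second baseline would absorb much of it, but the plan has neither. If frailty were instead classified at follow-up, the same bias would appear with the opposite sign.

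Frail patients are a stated interest: the target of 100 is justified by wanting to study frailty in a larger sample. The bias also runs against the plan's central hypothesis that rehabilitation as now delivered falls short on frailty. It could make rehabilitation look effective in frail patients when it is not, and the work is meant as preliminary data for a later grant.

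**Working it through.** **Inputs from the documents.** Two-sided 0.05, so 2.5% in the improving direction. Cohort 100, frail share 17%, giving 0.17 × 100 = 17 frail patients. Grip mean 28, SD 6.3 (women aged 50-59; kg assumed). Design difference 0.20 × 28 = 5.6.

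**Assumed, because the documents give no figure.** Retest correlation r of 0.95, 0.9, 0.8 and 0.7; correlation between frailty items; correlation of visit-to-visit fluctuations across items. There is no true change throughout. False improvement means p<0.05 in the improving direction.

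**The plan's own figure.** The stated 40 patients do not reproduce. If 6.3 is taken as the SD of differences, (1.96 + 0.84)² × 6.3² / 5.6² ≈ 10 (12 by exact t). That is a separate matter, and nothing below depends on it.

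**Step 1: selection on the tested measure alone.** For patients below a cut at standardised value z, the expected spurious gain is SD × (1 − r) × φ(z)/Φ(z). With a cut more than 20% below the mean, 0.8 × 28 = 22.4, z = (22.4 − 28)/6.3 = −0.89 and φ/Φ = 0.2687/0.187 = 1.437. The gain is 6.3 × 1.437 × (1 − r) = 9.05 × (1 − r): 0.45 at r = 0.95 and 2.72 at r = 0.7. Simulation gives 0.46 and 2.71.

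**Step 2: simulated results for grip, by definition of frail.** Each trial has 100 patients, classified at baseline and tested by paired t. Values are for r = 0.95 / 0.9 / 0.8 / 0.7.

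| Frail means | Spurious gain (kg) | False improvement (%) |
|---|---|---|
| 3 of 5, inter-item 0.2 | 0.15 / 0.28 / 0.57 / 0.88 | 5.1 / 5.9 / 7.7 / 11.2 |
| 3 of 5, inter-item 0.4 | 0.12 / 0.25 / 0.51 / 0.77 | 4.3 / 5.4 / 7.1 / 8.9 |
| 3 of 5, inter-item 0.6 | 0.11 / 0.23 / 0.44 / 0.66 | 4.1 / 5.0 / 6.5 / 8.2 |
| Grip or gait in lowest fifth (33 per 100) | 0.19 / 0.39 / 0.77 / 1.15 | 7.8 / 11.6 / 18.8 / 26.0 |
| Grip and gait in lowest fifth (7 per 100) | 0.34 / 0.74 / 1.39 / 2.15 | 5.7 / 8.5 / 12.7 / 17.8 |
| Grip alone below 22.4 (19 per 100) | 0.46 / 0.92 / 1.83 / 2.71 | 15.3 / 27.6 / 48.7 / 65.2 |
| Grip alone in lowest fifth (20 per 100) | 0.45 / 0.88 / 1.76 / 2.63 | 16.0 / 26.7 / 49.8 / 67.3 |

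The 3-of-5 rows fix prevalence at 17% and take fluctuations as independent across items. The two grip-and-gait rows assume an inter-test correlation of 0.3; a repeat run gave 7-27% (either) and 6-20% (both). In the grip-alone rows the Wilcoxon test gives similar rates (14.7-65.1%).

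**Step 3: variations on 3 of 5.**
- Lowest-fifth cut-offs on each item feeding the count: about 8-16 frail per 100, false improvement 4-9%.
- Fluctuations correlated 0.2 across items: gain 0.20-1.56 kg, false improvement 6.0-24.9%.

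**Step 4: the literal 20% reading.** Below 20% of predicted means below 0.20 × 28 = 5.6, so z = (5.6 − 28)/6.3 = −3.56 and the tail area is 0.00019, about 0.02 patients per 100.

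**Step 5: reference checks.** The whole-cohort paired t-test gives 2.1-2.8%, and whole-cohort prevalence stays at 17%. Classifying on two or more of the other four items gives a gain of −0.01 to 0.02 kg and 2.4-2.8% when fluctuations are independent. At fluctuation correlation 0.2 it gives 0.09-0.63 kg and 4.2-9.9%. The bias therefore comes from selecting on the tested measure and on fluctuations shared with it.

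**The case against.** The strongest case on the other side is that the effect is small where the plan is read coherently. The 20% phrase describes performance on tests, not patients, and comparing frailty with pre-frailty makes sense only under a count of characteristics. The phrase then most naturally sets an item cut-off feeding the count, and false improvement is 4-9%. Averaging three grip and gait trials removes within-visit error, though not month-to-month variation, so the high-correlation end is the more plausible one for grip. At r of 0.9 to 0.95 with independent fluctuations, 3 of 5 gives about 4-6%. The grip figures come from a norm for women in one age band, while the study enrols adults of both sexes and adjusts grip for gender and BMI. All of this stands, and it limits the size of the bias. It does not remove the mechanism, and the small figures themselves rely on independent fluctuations.

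A reader might infer that false improvement of 15-67% is to be expected. The documents do not support that: it needs the group to be chosen on the tested measure alone, whereas the plan refers to physiologic tests in the plural. A reader might also infer that the literal 20% reading leaves no frail subgroup at all. That is shown for grip only, because no norms are given for the other tests. Finally, a significance test inside the frail subgroup is inferred from the adjacent sentences, not stated.

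**Conclusion.** The point holds in a limited form. On the natural reading, the frail-subgroup comparison is biased toward improvement. For grip, against a nominal 2.5%, false improvement is about 4-11% under 3 of 5 with independent fluctuations, about 6-25% if fluctuations correlate 0.2, and about 6-27% if frail means low on either or both of grip and gait. These ranges rest on assumed correlations, and the bias tends to zero as retest correlation approaches 1. Every spurious gain found, at most about 2.7 kg, is below the 5.6 design difference. It would be wrong to extend the point to the whole-cohort tests or the whole-cohort prevalence comparison, which do not select on baseline values in this way. Severity is low, since this is a secondary analysis in a pilot; it is a cheap improvement.

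**What to change.** 1. In the Analysis plan, label the pre/post change in frail patients exploratory. Report it with intervals and no significance test, and state that regression to the mean inflates it, so an interval excluding zero is not evidence of benefit.
2. If a test is wanted, classify frailty at baseline on the other components only when testing one characteristic, for example two or more of the other four.
3. Keep the inferential pre/post and prevalence tests in the whole cohort.
4. Reconcile the 20% phrase with the three-of-five definition, and state that frailty is classified at baseline.

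The cost is wording, with no new visits or data. Under item 1 the subgroup loses its p-value, and the interval remains biased, which is why the caveat is needed. Under item 2 the subgroup differs by outcome. It contains every 3-of-5 frail patient but grows to about 24-30 per 100, so with 17 frail about 7-13 are not 3-of-5 frail. Some bias also remains if a bad week lowers several measures together (false improvement about 4-10% at fluctuation correlation 0.2).
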